6.3.4.3. Analyses of exacerbations in relation to morning e-diaries

Among morning e-diary alerts the frequency distribution of the following groups will be tabulated (refer to [Figure 1](#) dashed boxes):

1. Potential event not confirmed by phone call/or at the study site (unconfirmed alerts, box 1),
2. Potential event confirmed by phone call/or at the study site, without site visit, with medical records confirming exacerbation (missed AECOPD visits with medical records, box 2),

CONFIDENTIAL201112 (EPI-NTHI-001 BOD APA)
Statistical Analysis Plan Amendment 2 Final

3. Potential event confirmed by phone call/or at the study site, without site visit and without medical records (missed AECOPD visits without medical records, box 3).
4. Potential event confirmed by phone call/or at the study site, with site visit but not confirmed by study investigator (unconfirmed AECOPD visit, box 4),
5. Potential event confirmed by phone call/or at the study site, with site visit and confirmed by study investigator (AECOPD event, box 5),

[figure not shown]
Reasons for inconsistencies between morning e-diary alert and no confirmation by phone call, reasons for missing study visit after phone call confirmation, and reasons for inconsistencies between phone call confirmation and study visit will be tabulated.

In absence of morning diary alert the percentage of spontaneous visits confirming exacerbation or missed AECOPD visit with medical record confirming AECOPD will be tabulated ([Figure 1](#), boxes 6 and 7).

CONFIDENTIAL

201112 (EPI-NTHI-001 BOD APA)
Statistical Analysis Plan Amendment 2 Final

Figure 1 Workflow of study assessment for AECOPD

CONFIDENTIAL

201112 (EPI-NTHI-001 BOD APA)
 Statistical Analysis Plan Amendment 2 Final

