6.4.1. End date of AECOPD using EXACT-PRO

Descriptive statistics (N, mean, median, standard deviation, minimum and maximum, first and third quartiles) on the average length of AECOPD episodes, as estimated through the EXACT-PRO (section 12), will be presented, for any, mild, moderate and severe AECOPD.

The frequency distribution of exacerbation confirmed at site visit or through medical records (with or without morning symptoms diary alert) will be tabulated versus EXACT-PRO exacerbations.

Descriptive statistics (N, mean, median, SD, minimum, maximum, first and third quartiles) for the EXACT daily scores will be tabulated at baseline, during the day before exacerbation, at exacerbation onset and at recovery according to investigator judgement. These statistics will be reported overall and for any mild, moderate or severe exacerbation visit.

Graphs detailing the EXACT-PRO scores before, during and after exacerbation onset as defined clinically will be also presented.

Difference from baseline, with 95% CI, of EXACT score measured at stable scheduled visit will be plotted.

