11.5. Methodology for computing CI

- All CI computed will be two-sided at 95% significant level.
- The exact 95% CIs for a proportion within a group will be calculated using Clopper Pearson method [[Clopper 1934](#)].

12. ANNEX 2: AECOPD DEFINITION AND CALCULATION RULE**12.1. Definition, onset, recovery, duration of an AECOPD event**

AECOPD events are confirmed according to investigator judgment after an AECOPD visit which is aimed to exclude worsening in symptoms not related to an AECOPD event.

AECOPD visits are scheduled after an electronic Diary Card alert confirmed by the investigator (by phone call or at the study site) or after spontaneous site visits due to worsening symptoms without any alert.

Electronic Diary Card alerts refer to daily symptoms recorded the morning after (also called morning symptoms). Alerts are based on the Anthonisen criteria:

- Worsening of two or more of the following major symptoms for at least two consecutive days*^{***}: dyspnea, sputum volume, sputum purulence (colour)

Or

- Worsening of any major symptom together with any of the following minor symptoms for at least two consecutive days*^{***}: sore throat, colds (nasal discharge and/or nasal congestion), fever (oral temperature $\geq 37.5^{\circ}\text{C}$) without other cause, increased cough, increased wheeze.

** The same two symptoms do not have to be present on both days as long as at least one major symptom is present on both days.*

CONFIDENTIAL

201112 (EPI-NTHI-001 BOD APA)
 Statistical Analysis Plan Amendment 2 Final

AECOPD onset will be defined as the first day of the two consecutive days of worsening symptoms.

AECOPD recovery will be determined/confirmed by the investigator/delegate during (a) follow-up phone call(s) which will take place every 2 weeks until the AECOPD has resolved. The end date will be based on when the investigator/delegate determines that the AECOPD symptoms have resolved. In determining this end date, consideration will be given to symptoms recorded in the electronic Diary Card and patient assessment during the phone calls.

AECOPD duration will be defined as the number of days from AECOPD onset (included) and AECOPD recovery (not included).

Duration = date2 – date1 + 1,

with date2: AECOPD recovery date,

date1: AECOPD onset date

12.2. Recovery and duration of an exacerbation according to EXACT-PRO:

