An EXACT-PRO AECOPD event is defined as a 12 point increase above baseline for 2 consecutive days, or a nine point increase for 3 consecutive days.

The baseline EXACT-PRO score is calculated as the average daily EXACT-PRO score over days 14 to 8 preceding AECOPD symptomatic onset.

AECOPD recovery according to EXACT-PRO corresponds to the day at which the EXACT-PRO score return to its baseline value (or below) [Mackay AJ, Donaldson GC, Patel AR, Singh R, Kowlessar B, Wedzicha JA. Detection and severity grading of COPD exacerbations using the exacerbations of chronic pulmonary disease tool (EXACT). *Eur Respir J*. 2014;43(3):735-44.].

The AECOPD duration according to EXACT-PRO will be defined as the number of days from AECOPD onset (included) and AECOPD recovery according to EXACT-PRO (not included).

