12.2.1. EXACT-PRO baseline score at enrolment

An EXACT-PRO baseline score at enrolment will be computed as the mean within-patient score over 7 days, with data present for a minimum of 4 of the 7 days. If fewer than 4 days of data are available, the EXACT baseline score cannot be calculated.

CONFIDENTIAL201112 (EPI-NTHI-001 BOD APA)
Statistical Analysis Plan Amendment 2 Final**12.3. Time between 2 e-diary signals for exacerbations/evaluation of baseline symptom score:**

The minimum duration between 2 e-diary signals with distinct baseline value is 15 days, which is the minimal period for which a new full exacerbation-free baseline can be calculated for the next e-diary episode.

If a new worsening of symptoms occurs between 6 and 14 days after the end of a previous exacerbation, the baseline period used will be the same baseline as the one of the original exacerbation. Therefore, it will last until the daily symptom count score has gone below the baseline symptom score of the previous event.

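### SAP 12.2 ties EXACT-PRO event detection to an AECOPD onset, so the 6.4.1 cross-tabulation undercounts EXACT-only events

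*SAP*

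**What the plan says.** SAP section 12.2 gives the event rule: "An EXACT-PRO AECOPD event is defined as a 12 point increase above baseline for 2 consecutive days, or a nine point increase for 3 consecutive" (that is, 3 days). The sentence after it fixes the baseline: "The baseline EXACT-PRO score is calculated as the average daily EXACT-PRO score over days 14 to 8 preceding AECOPD symptomatic onset". Section 12.2.1 then defines a second baseline: "An EXACT-PRO baseline score at enrolment will be computed as the mean within-patient score over 7 days, with data present for a minimum of 4" (out of the 7). It does not say which 7 days are meant or what this score is used for.

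On onset, section 12.1 states: "AECOPD onset will be defined as the first day of the two consecutive days of worsening symptoms". The planned comparison is in section 6.4.1: "The frequency distribution of exacerbation confirmed at site visit or through medical records (with or without morning symptoms diary alert) will be tabulated versus EXACT-PRO" events. Its clinical side is limited to events confirmed at a visit or through medical records. Section 6.3.4.3 lists diary episodes that fall outside that margin: alerts rejected on contact (box 1), events accepted on contact but with neither visit nor records (box 3), and visits at which the investigator did not confirm the event (box 4).

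The protocol (section 3) has EXACT-PRO completed every evening throughout the study, and section 3.1 mentions its potential for identifying events as well as their resolution. The tertiary objective itself concerns only the end date of an AECOPD.

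**The concern.** A cross-tabulation of two ways of finding exacerbations is informative only if each can find events that the other misses. Here the EXACT-PRO side needs a baseline, and the stated baseline needs an AECOPD onset date. A stretch of diary with no such onset has no baseline, so no rise above it can be measured, however large.

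What is at stake is how the table is read. Worsening that the evening diary records but that never becomes an AECOPD on the clinical side is what a daily patient-reported tool might add. If the derivation leaves it out, the table can look like support for EXACT-PRO against the investigator when part of that pattern comes from the definition.

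**Working it through.** No sample size, interval or agreement figure in the documents depends on this definition, so there is no plan figure to reproduce. The check has two parts: tracing the definitions, then showing what the affected cell controls.

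**1. Tracing the definitions.** Three readings can be put to the text.

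| Reading | Baseline available when | EXACT-PRO yes, confirmed no |
|---|---|---|
| A. 12.2 baseline; onset means a confirmed AECOPD | A confirmed AECOPD exists | Empty |
| B. 12.2 baseline; onset also covers unconfirmed or undocumented alerts (boxes 1, 3, 4) | Any such alert or event exists | Can be filled, but only around an alert |
| C. 12.2.1 enrolment baseline used for detection | At least 4 of 7 enrolment days have data | Can be filled on any diary day |

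- Support for A: SAP 12.1 opens by describing AECOPD events as confirmed by the investigator. Protocol 3.1.1.1 has the investigator determine onset and records start and end dates for confirmed AECOPD.
- Support for B: the onset sentence in SAP 12.1 refers only to worsening symptoms. SAP 12.4 and 12.5 also use the term AECOPD for potential and unconfirmed episodes, and protocol 3.1.1 captures an onset date when a visit is scheduled.
- Against C as the intended reading: 12.2.1 assigns no detection role and gives no reset rule. The enrolment score has another natural use, the plot in 6.4.1 of change from baseline at stable visits.

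Reading B widens the cell but does not complete it. The alerts come from the morning symptom questionnaire, a separate instrument from the evening EXACT-PRO. An EXACT-PRO rise with no morning alert and no reported event still has no onset and no baseline. So on both readings that use the stated baseline, the cell is empty or truncated.

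Two further gaps appear. No window is given for matching an EXACT-PRO event to a clinical one. SAP 12.3 sets spacing and baseline-reuse rules for e-diary signals, but nothing comparable is given for EXACT-PRO events.

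**2. What the cell controls.** Let a = events found by both, b = EXACT-only, c = clinical-only.

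- Share of EXACT-PRO events clinically confirmed = a/(a+b). With b = 0 this is 100% whatever the diary contains.
- Share of clinical events meeting the EXACT-PRO criteria = a/(a+c). This does not involve b.

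To show how far the first share depends on b, take 160 clinical events: the protocol's 80% completion applied to 200 enrolled gives 200 × 0.8 = 160 subjects, and Table 13 has a row at 1 AECOPD per subject per year. The documents give neither the fraction of clinical events that are EXACT-positive nor the number of EXACT-only events. Both are assumptions here.

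| EXACT-positive clinical events (a) | b = 0 | b = 20 | b = 40 | b = 80 | b = 160 |
|---|---|---|---|---|---|
| 30% (a = 48) | 100% | 71% | 55% | 38% | 23% |
| 50% (a = 80) | 100% | 80% | 67% | 50% | 33% |
| 70% (a = 112) | 100% | 85% | 74% | 58% | 41% |

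For example, 80/(80+40) = 67%. The spread shows that a/(a+b) is governed by the cell the definition suppresses. It is not an estimate for this study.

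**The case against.** The strongest reply is that the SAP leaves something unsaid but makes nothing impossible. A reader might infer that EXACT-only events cannot exist under this plan, that their cell is zero by construction, and that the confirmed share is fixed at 100%. The documents do not support that. Symptomatic onset is not expressly limited to confirmed AECOPD, so box 1, 3 and 4 episodes could have an onset, a baseline and an EXACT-PRO event while being negative on the clinical side. Section 12.2.1 sits under 12.2, and using its baseline for detection is neither stated nor excluded. This part of the reply stands, and it is why the point is framed as empty or truncated.

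A reader might also infer that a planned agreement measure will be inflated. It will not be: the current SAP plans a frequency table only. The kappa for this comparison appears in SAP version 1 and is absent from both amendments. The table can still legitimately be read in the other direction, as the share of confirmed events that meet the EXACT-PRO criteria. The mock layouts are in a separate document, so the intended display cannot be checked.

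Finally, a pre-onset baseline suits the recovery and duration purpose of 12.2, and all analyses are descriptive. Both statements are correct, and both limit the consequence. Neither supplies a baseline for diary periods without an onset, which a full cross-tabulation needs.

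**Conclusion.** The point holds in a limited form. The only baseline linked to the EXACT-PRO event rule requires an AECOPD onset. In the 6.4.1 table, EXACT-only events are therefore absent if onset means a confirmed AECOPD, and undercounted if it also covers unconfirmed alerts. The table cannot show how many EXACT-PRO events are clinically confirmed. The share of confirmed events meeting the EXACT-PRO criteria is not distorted by this.

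The conclusion assumes that the stated baseline is the one programmed. If the enrolment baseline were used for detection, the cell could fill, but the SAP would need to say so. The size cannot be computed from the documents. The effect is confined to one tertiary descriptive table; the recovery and duration analysis, which starts from a clinical onset, is unaffected. The correction is worth making because it is cheap and changes what the table can be said to show.

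**What to change.** For the 6.4.1 table, derive EXACT-PRO events on all diary days from Visit 1 to Visit 3 against a baseline that does not depend on clinical onset. The 12.2.1 score can serve, provided the SAP states which 7 days it covers and gives a reset rule that excludes exacerbation and recovery days. State in advance the window within which an EXACT-PRO event counts as matched to a confirmed AECOPD, and report matched, clinical-only and EXACT-only events. Keep the day 14 to 8 baseline for recovery and duration.

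If that is not wanted, restrict the table to the share of confirmed AECOPD that meet the EXACT-PRO criteria, and state that it does not assess EXACT-only events.

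The cost is SAP wording and some programming on diary data already collected. There are two small downsides. Two EXACT-PRO baselines must be clearly labelled. And a baseline reset only at scheduled visits, which protocol Table 6 places 175 to 203 days apart, may drift and produce spurious EXACT-only events.

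### SAP 12.2 and 6.4.1 derive an EXACT-PRO length for clinical AECOPD of any severity without requiring an EXACT event, or a rise, before recovery, so an unchanged score can be coded as a 0-day episode

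*SAP*

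**What the plan says.** Protocol 9.7 leaves the EXACT-PRO end date to an algorithm to be set out in the SAP. That algorithm is SAP 12.2:

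- **Event criterion:** "a 12 point increase above baseline for 2 consecutive days, or a nine point increase for 3 consecutive days".
- **Baseline:** "average daily EXACT-PRO score over days 14 to 8 preceding AECOPD symptomatic onset".
- **Recovery:** "AECOPD recovery according to EXACT-PRO corresponds to the day at which the EXACT-PRO score return to its baseline value (or below").
- **Length:** "number of days from AECOPD onset (included) and AECOPD recovery according to EXACT-PRO (not included").

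The clock starts at clinical onset, which 12.1 takes from symptoms: "AECOPD onset will be defined as the first day of the two consecutive days of worsening symptoms". SAP 6.4.1 then gives descriptive statistics of episode length "as estimated through the EXACT-PRO (section 12), will be presented, for any, mild, moderate and severe AECOPD". Severity is the investigator's CRF entry (12.6); the SAP defines no EXACT severity grade. Section 6.4.1 also cross-tabulates confirmed exacerbations against EXACT-PRO exacerbations, so it foresees clinical AECOPD that are not EXACT events. Neither section says what EXACT length those episodes receive.

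**The concern.** The recovery and length sentences in 12.2 do not refer back to the event criterion stated above them. They ask for no earlier rise, and one daily score at or below baseline is enough. Both the baseline and the clock hang on clinical onset, and the reported episodes are clinical ones.

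Where EXACT did not move, there is nothing to recover from. A daily score that has not shifted lies at or below the mean of seven earlier scores about as often as above it, so the rule can be satisfied on the onset day itself. With onset counted and recovery not counted, the length is then 0.

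The first tertiary objective is to assess EXACT-PRO for determining when an AECOPD ends. If lengths that mean the score never rose are averaged with genuine recovery times, the summary no longer describes end dates, and a comparison with the investigator's end date is hard to interpret.

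**Working it through.** The documents give no figure for EXACT length or for the share of AECOPD without an EXACT rise, so there is no planned number to reproduce. The check asks what the written rule returns.

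**Inputs from the SAP:** baseline is the mean of 7 daily scores (days 14 to 8 before onset); recovery is the first day with score at or below baseline; onset day counted, recovery day not counted; event criterion as in 12.2.

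**Assumptions, not in the documents:** normal daily scores; within-patient day-to-day SD 3, 5 or 8 points; lag-1 autocorrelation 0, 0.5 or 0.8; mean rise 0 to 8 points lasting 10 days.

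**Step 1, closed form for independent days.** The onset-day score minus the baseline mean has mean equal to the rise r and variance SD² × (1 + 1/7). Length is 0 when this difference is at or below zero:

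P(length 0) = Φ(−r / (SD × √(8/7)))

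For SD 5 the denominator is 5 × 1.069 = 5.345. A 2-point rise gives Φ(−0.374) = 0.354, and an 8-point rise gives Φ(−1.497) = 0.067.

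| Mean rise | SD 3 | SD 5 | SD 8 |
|---|---|---|---|
| 0 | 0.500 | 0.500 | 0.500 |
| 2 | 0.266 | 0.354 | 0.408 |
| 4 | 0.106 | 0.227 | 0.320 |
| 6 | 0.031 | 0.131 | 0.241 |
| 8 | 0.006 | 0.067 | 0.175 |

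**Step 2, simulation with autocorrelation and whole-number scores** (200,000 episodes per setting).

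- With no rise, P(length 0) is 0.503 to 0.510 for every SD and autocorrelation tried, so this figure does not depend on those assumptions.
- Among no-rise episodes that do not meet the event criterion, the median length is 0 days and 60% to 76% have length 0 or 1 day.
- The table covers all episodes with a given mean rise. Among those that miss the event criterion, P(length 0) is 0.51 to 0.64 with no mean rise and 0.01 to 0.41 with an 8-point mean rise.

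**Step 3, counting rule.** In 12.2, recovery on the onset day gives 0 days. Section 12.1 uses the same included and not-included wording for investigator-dated episodes, but its formula is date2 − date1 + 1, which gives 1 day for the same dates. The wording and the formula in 12.1 disagree by one day, and whichever is programmed for EXACT decides between 0 and 1.

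**Step 4, would restricting to EXACT events be enough?** No. If the search still starts at clinical onset, 0-day lengths remain in under 1% to about 33% of episodes meeting the criterion. The upper end occurs at SD 8 with no mean rise, where noise alone meets the criterion in 12% of episodes. If the EXACT rise starts on the onset day or later and the search begins only after the criterion is met, the shortest possible length is 2 days.

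**Illustration only.** If a fraction f of AECOPD had a mean length of 2 days through lack of a rise and the rest averaged 13 days, the reported mean would be 2f + 13(1 − f): 10.8 days for f = 0.2, 8.6 for 0.4 and 6.4 for 0.6. None of these inputs comes from the documents.

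**The case against.** The strongest counter-argument is the word 'return'. A score that never left baseline cannot return to it, and 12.2 opens with the event definition, so one can read the section as giving no EXACT recovery date to an episode without a rise. That reading is fair: a reader might infer that the SAP expressly orders the rule to be applied to no-rise episodes, and it does not. But it does not exclude them either, and 6.4.1 reports length by clinical severity with no restriction. Two programmers could produce different tables, and the literal coding produces the artefact.

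Second, a mean shift of exactly zero is the extreme case. Diary alerts need worsening of a major symptom on two consecutive days, and EXACT-PRO covers breathlessness, cough and sputum, so some rise may be common. This stands: failing the event criterion is not the same as having no rise, and the one-half figure should not be applied to every AECOPD that is not an EXACT event.

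Third, 6.4.1 also reports N, median, quartiles and minimum, the cross-tabulation, EXACT scores at onset and recovery, and score graphs. A cluster of zeros might be noticed. It could still not be separated from the reported mean.

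Fourth, restricting length to EXACT events conditions on EXACT having responded. This is a real cost, which is why the number left out has to be reported.

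**Conclusion.** The point holds as a defect in the derivation rule. Coded as written, an AECOPD with no change in EXACT score receives 0 days (or 1 day under the 12.1 formula) about half the time. With a rise the share is lower and depends on the rise, SD and autocorrelation, none of which the documents give. The effect on the reported length is downward, but its size cannot be estimated because the share of AECOPD without an EXACT rise is unknown; the mixed means above are illustrative.

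A reader might also infer that mild AECOPD would be affected most. The documents do not support that. Severity is graded by the treatment or care required (Protocol Table 2, SAP 12.6), not by symptom score, and nothing in them shows smaller EXACT rises in mild episodes.

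The consequence is confined to a tertiary objective, and SAP section 7 treats all analyses as descriptive. The change is still worth making, because the affected quantity is the one that objective is about.

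**What to change.** In SAP 12.2, derive the EXACT end date and length only for AECOPD that meet the 12-point/2-day or 9-point/3-day criterion, and search for the return to baseline only after the day the criterion is met. State the window around clinical onset within which an EXACT event counts as belonging to the AECOPD.

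In SAP 6.4.1, report the number and percentage of AECOPD with no EXACT event, overall and by severity, as having no EXACT end date, and leave them out of the length statistics. That percentage is itself informative about whether EXACT-PRO can be used to date the end of an AECOPD.

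Reconcile the not-included wording in 12.1 with its date2 − date1 + 1 formula, and state which count applies to the EXACT length.

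The cost is SAP wording, one condition in the derivation and one added count. EXACT length will be summarised on fewer AECOPD, only those in which EXACT responded. A single low score after the criterion is met could still end an episode; this change does not address that.
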